4003187	Acute myelomonocytic leukemia, FAB M4
135768	Acute monocytic leukemia
4003184	Acute panmyelosis with myelofibrosis
4082485	Acute monoblastic leukemia
4189938	Acute monocytic/monoblastic leukemia
4173970	Acute eosinophilic leukemia
132850	Myeloid leukemia in remission

Observation domain

concept_id	concept_name
4304355	Acute myeloid leukemia with abnormal marrow eosinophils
4304199	Acute myeloid leukemia, minimal differentiation
4304356	Acute myeloid leukemia without maturation
4304051	Acute myeloid leukemia with maturation
4029177	Acute myeloid leukemia with myelodysplasia-related changes
4028713	Acute myeloid leukemia, t(8;21) (q22;q22)
4029663	Acute myeloid leukemia, 11q23 abnormalities
4030263	Therapy-related acute myeloid leukemia and myelodysplastic syndrome
4031360	Acute myeloid leukemia, M6 type
4073533	Acute myeloid leukemia, no ICD-O subtype
4265011	Acute myeloid leukemia with recurrent genetic abnormality
4264447	Acute myeloid leukemia with multilineage dysplasia following a myelodysplastic syndrome or myelodysplastic syndrome/myeloproliferative disorder
4288090	Acute myeloid leukemia with multilineage dysplasia without antecedent myelodysplastic syndrome
4287472	Therapy-related acute myeloid leukemia and myelodysplastic syndrome, alkylating agent-related type
4265012	Therapy-related acute myeloid leukemia and myelodysplastic syndrome, topoisomerase type II inhibitor-related type
4184848	Acute myeloid leukemia
42872921	Mixed phenotype acute leukemia B/myeloid
42872922	Mixed phenotype acute leukemia T/myeloid
42872933	Acute myeloid leukemia with t(6;9)(p23;q34); DEK-NUP214
42872934	Acute myeloid leukemia with inv(3)(q21q26.2) or t(3;3)(q21;q26.2); RPN1-EVI1
42872942	Acute myeloid leukemia (megakaryoblastic) with t(1;22)(p13;q13); RBM15-MKL1
45771384	Acute myeloid leukemia with mutation of CEBPA (CCAAT enhancer binding protein alpha) gene
45766616	Acute myeloid leukemia with mutated NPM1

	D2.2.3 – Study Protocol for C1-001	
	Author(s): [name], [name], [name], [name]	Version: 2.0 - Final
	Dissemination level: Public	

37110871	Acute myeloid leukemia with t(8;16)(p11;p13) translocation
42535969	Acute myeloid leukemia with FMS-like tyrosine kinase-3 mutation
37204375	Acute myeloid leukemia with BCR-ABL1
37204557	Acute myeloid leukemia with mutated RUNX1
37312067	Acute myeloid leukemia with biallelic mutation of CEBPA (CCAAT enhancer binding protein alpha) gene
46273391	History of acute myeloid leukemia

Acute lymphocytic leukaemia

Clinical description

Overview

Acute lymphocytic leukaemia (also called “ALL”, acute “lymphoblastic” leukaemia) is a type of cancer that affects white blood cells. In ALL, the process of development of blood cells is faulted, with immature, non-functioning leukemic cells being released from hematopoietic progenitors in the bone marrow or lymphatic system. This leads to anaemia, granulocytopenia, and thrombocytopenia, and causes symptoms of fatigue, weakness, breathlessness, infection, and haemorrhage. ALL progresses quickly and aggressively, with immediate treatment being required.

ALL is the most frequent neoplastic disease in children, with most of the cases being diagnosed in children aged 3-4 years. In adults, incidence ranges from 0.7 to 1.8/100 000 per year, being slightly higher in adolescents and young adults and the elderly.

Presentation

Common symptoms why patients first seek medical advice include fatigue and feeling breathless, repeated infections over a short time and unusual and frequent bleeding. Other symptoms can comprise pale, easily bruised skin; high temperature and night sweats; bone and joint pain as well as swollen lymph nodes, abdominal pain and unintentional weight loss. In some cases the central nervous system (CNS) is also affected, with neurological symptoms including headaches, seizures, blurred vision or dizziness being reported.

Assessment

- Peripheral blood counts: White blood cell (WBC) count in ~40% of ALL patients is reduced or normal. In 8% of ALL patients, no circulating leukemic blast cells were observed. Peripheral blood typically shows anaemia, thrombocytopenia, and neutropenia: Nearly 30% of patients have haemoglobin levels below 7–8 g/dL. Platelet counts below the critical number of $20 \times 10^9/L$ and neutropenia (neutrophils $<0.5 \times 10^9/L$), are each noted in ~20% of adults with ALL, respectively.
- Bone marrow biopsy: To assess immunologic, cytogenetic, and genomic markers. In ALL, the bone marrow is typically packed with leukemic blast cells with >90% in ~70% of patients, and normal hemopoietic elements are greatly reduced or absent.
- Lumbar puncture: CNS leukaemia is diagnosed if ≥ 5 cells/ μL or leukemic blast cells were observed by morphology in cerebrospinal fluid. Lumbar puncture is conducted either when remission is achieved or before treatment starts, and restricted to patients with an adequate platelet count.
- Immunological assays for classification into B-cell lineage or T-cell lineage ALL leukaemias. B-Cell Lineage ALL: 70% of adult ALLs are of B-cell origin, T-Cell Lineage ALL: ~25% of adult ALLs are of T-cell

	D2.2.3 – Study Protocol for C1-001	
	Author(s): [name], [name], [name], [name]	Version: 2.0 - Final
	Dissemination level: Public	

lineage, Biphenotypic or Mixed Leukaemia, which express markers of both lymphoid and myeloid lineages on the same leukemic cells

- Cytogenetic and molecular analyses to define ALL subtypes, typically via standard cytogenetics, fluorescence in situ hybridization, and reverse transcriptase polymerase chain reaction.

Plan

- Pre-phase therapy: glucocorticoids (alone or combination) for ~5–7 days
- Induction therapy: typically vincristine, glucocorticoids, anthracyclines with or without cyclophosphamide or cytarabine. Adult ALL: L-Asparaginase is the only ALL-specific drug, targeted therapies including Tyrosine-kinase inhibitors (TKI, e.g. imatinib, dasatinib, nilotinib, ponatinib) for Ph+ ALL, immunological therapies (e.g. rituximab, blinatumomab)
- Post-remission consolidation: six to eight courses of high-dose methotrexate and/or cytarabine
- Maintenance treatment: 6-mercaptopurine and methotrexate plus intrathecal therapy, typically for 2–2.5 years. For Ph+ ALL maintenance includes TKI
- Stem Cell Transplantation is an essential part of the treatment strategy for adult ALL for high-risk patients.

Prognosis

Highly age-related, with cure rates of ~90% in children, decreasing to <10% in elderly or frail patients

MedDRA PTs

N/A

Disqualifiers

N/A

Strengtheners

- Minimal residual disease (MRD) during therapy
- Stem cell transplantation
- Diagnosis in young children
- previous chemotherapy, genetic disorders e. g. Down Syndrome, weakened immune system (HIV, AIDS)

Preliminary code list

Condition domain

concept_id	concept_name
36712834	Acute lymphoid leukemia relapse
36712835	Refractory acute lymphoid leukemia
136656	Subacute lymphoid leukemia
4139054	Subacute lymphoid leukemia in remission
37018868	Disorder of central nervous system co-occurrent and due to acute lymphoid leukemia in remission
37018869	Disorder of central nervous system co-occurrent and due to acute lymphoid leukemia
141816	Acute lymphoid leukemia in remission
134305	Acute lymphoid leukemia

	D2.2.3 – Study Protocol for C1-001	
	Author(s): [name], [name], [name], [name]	Version: 2.0 - Final
	Dissemination level: Public	

4173963	B-cell acute lymphoblastic leukemia
4082461	Precursor B-cell acute lymphoblastic leukemia
4079280	Common acute lymphoblastic leukemia
4079281	Null cell acute lymphoblastic leukemia
4082462	T-cell acute lymphoblastic leukemia
4153344	Acute lymphoblastic leukemia, transitional pre-B-cell
4299143	Leukemic infiltration of skin (T-cell lymphoblastic leukemia)
4221907	Precursor T cell lymphoblastic leukemia/lymphoblastic lymphoma
4138008	Philadelphia chromosome-positive acute lymphoblastic leukemia
4138752	Precursor B-cell acute lymphoblastic leukemia in remission
4143997	T-cell acute lymphoblastic leukemia in remission
37017893	Philadelphia chromosome-negative precursor B-cell acute lymphoblastic leukemia
37109936	B lymphoblastic leukemia lymphoma with t(9;22) (q34;q11.2); BCR-ABL 1
3654647	B lymphoblastic leukemia lymphoma with t(5;14)(q31;q32); IL3-IGH
3654648	B lymphoblastic leukemia lymphoma with t(v;11q23); MLL rearranged
3654649	B lymphoblastic leukemia lymphoma with t(12;21) (p13;q22); TEL/AML1 (ETV6-RUNX1)
3654650	B lymphoblastic leukemia lymphoma with t(1;19)(Q23;P13.3); E2A-PBX1 (TCF3/PBX1)
3654651	B lymphoblastic leukemia lymphoma with hypodiploidy
3654653	B lymphoblastic leukemia lymphoma with hyperdiploidy
4003188	Adult T-cell leukemia/lymphoma
4081867	Acute biphenotypic leukemia
4227963	Precursor T-cell lymphoblastic lymphoma
134596	Lymphoid leukemia in remission

Observation domain

concept_id	concept_name
4030260	Precursor cell lymphoblastic leukemia
4029662	Precursor B-cell lymphoblastic leukemia
4030261	Precursor T-cell lymphoblastic leukemia
4264448	Precursor B-lymphoblastic leukemia/lymphoblastic lymphoma
4288091	Precursor T cell lymphoblastic leukemia/lymphoblastic lymphoma
4189936	Acute lymphoblastic leukemia - category
4143821	Philadelphia chromosome-positive acute lymphoblastic leukemia
42872925	B lymphoblastic leukemia / lymphoma - category
42872954	B lymphoblastic leukemia lymphoma, no ICD-O subtype
42872955	B lymphoblastic leukemia lymphoma with t(9;22)(q34;q11.2); BCR-ABL1
42872956	B lymphoblastic leukemia lymphoma with t(v;11q23); MLL rearranged
42872957	B lymphoblastic leukemia lymphoma with t(12;21)(p13;q22); TEL-AML1 (ETV6-RUNX1)
42872958	B lymphoblastic leukemia lymphoma with hyperdiploidy
42872959	B lymphoblastic leukemia lymphoma with hypodiploidy (Hypodiploid ALL)

	D2.2.3 – Study Protocol for C1-001	
	Author(s): [name], [name], [name], [name]	Version: 2.0 - Final
		Dissemination level: Public

42872960	B lymphoblastic leukemia lymphoma with t(5;14)(q31;q32); IL3-IGH
42872961	B lymphoblastic leukemia lymphoma with t(1;19)(q23;p13.3); E2A-PBX1 (TCF3-PBX1)
45766617	T lymphoblastic leukemia/lymphoma
37204662	NK-lymphoblastic leukemia/lymphoma
37204838	B-lymphoblastic leukemia lymphoma BCR-ABL1-like
37206196	B lymphoblastic leukemia lymphoma with iAMP21

	D2.2.3 – Study Protocol for C1-001		
	Author(s): [name], [name], [name], [name]		Version: 2.0 - Final
	Dissemination level: Public		

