17. ANNEXES

Appendix I: Definitions of study outcomes

Follicular lymphoma

Clinical description

Overview

FLs are the second leading Non-Hodgkin's lymphomas (NHL), makes up 22% of NHL worldwide. This type of lymphoma can be diagnosed accurately on morphologic findings alone: B-cell in follicular centre.

Confirmation of B-cell immunophenotype (monoclonal immunoglobulin light chain, CD19, CD20, CD10 and BCL6 positive, and CD5 and CD23 negative) and the existence of the t(14;18) and abnormal expression of BCL-2 protein are confirmatory (85%).

The major differential diagnosis is between lymphoma and reactive follicular hyperplasia. The coexistence of DLBCL must be considered. Patients with FL are often subclassified, or graded, into those with predominantly small cells, those with a mixture of small and large cells, and those with predominantly large cells.

Presentation

Presentation for FL is with new, painless lymphadenopathy. Multiple sites of lymphoid involvement are typical, and unusual sites such as epitrochlear nodes are sometimes seen. However, essentially any organ can be involved, and extranodal presentations do occur. Many of these patients are diagnosed incidentally or at a time when their lymphoma is not causing symptoms or signs of organ function impairment. Most patients do not have an elevated LDH or fevers, night sweats, or weight loss (<20%). Transformation to DLBCL does occur at a rate of ~3% per year and can be associated with these signs/symptoms.

Assessment

Diagnosis: Lymph node biopsy.

Staging is typically done with CT scans of the chest, abdomen and pelvis, as well as the neck if neck disease is suspected, although PET/CT scans can be helpful in cases where disease transformation is suspected.

Grading

The WHO Classification adopted grading from 1 to 3 based on the number of centroblasts, or large cells, counted per high power field (hpf):

grade I, from 0 to 5 centroblasts/hpf;

grade II, from 6 to 15 centroblasts/hpf;

grade III, >15 centroblasts/hpf.

Grade III has been subdivided into grade IIIa, in which centrocytes predominate, and grade IIIb, in which there are sheets of centroblasts.

While this distinction cannot be made simply or very reproducibly, these subdivisions do have prognostic significance. Grade IIIb FL is an aggressive disease and considered most similar to Diffuse large B-cell lymphoma (DLBCL) and treated as such with curative intent.

	D2.2.3 – Study Protocol for C1-001	

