44808015	Follicular lymphoma grade 1
44814156	Follicular lymphoma grade 2
44808028	Follicular lymphoma grade 3
44808117	Follicular lymphoma grade 3a
44808118	Follicular lymphoma grade 3b
4146024	Malignant lymphoma - centrocytic
4119131	Nodular malignant lymphoma, lymphocytic - well differentiated
4121331	Nodular malignant lymphoma, lymphocytic - intermediate differentiation
4146027	Malignant lymphoma, mixed lymphocytic-histiocytic, nodular
4146031	Malignant lymphoma, lymphocytic, poorly differentiated, nodular
438698	Malignant lymphoma of lymph nodes of head, face AND/OR neck
435753	Malignant lymphoma of intrathoracic lymph nodes
200349	Malignant lymphoma of intra-abdominal lymph nodes
441521	Malignant lymphoma of lymph nodes of axilla AND/OR upper limb
192560	Malignant lymphoma of lymph nodes of inguinal region AND/OR lower limb
195195	Malignant lymphoma of intrapelvic lymph nodes
200343	Malignant lymphoma of spleen
132841	Malignant lymphoma of lymph nodes of multiple sites
435492	Nodular lymphoma of intrathoracic lymph nodes
200338	Nodular lymphoma of intra-abdominal lymph nodes
198088	Nodular lymphoma of intrapelvic lymph nodes
198374	Nodular lymphoma of spleen
320347	Nodular lymphoma of lymph nodes of multiple sites
440058	Malignant lymphoma of extranodal AND/OR solid organ site
194878	Nodular lymphoma of extranodal AND/OR solid organ site
4038838	Non-Hodgkin's lymphoma (clinical)
4149840	Nodular lymphoma

Observation domain

concept_id	concept_name
4017277	Malignant lymphoma, follicular AND/OR nodular
4200880	Follicular low grade B-cell lymphoma morphology
4265301	Follicular lymphoma, cutaneous follicle center sub-type
4265735	Follicular lymphoma, diffuse follicle center sub-type, grade 1
4288232	Follicular lymphoma, diffuse follicle center cell sub-type, grade 2
4230587	Follicular lymphoma, grade 3
4188203	Follicular lymphoma, grade 1
4204524	Follicular lymphoma, grade 2
4205271	Follicular lymphoma
37116892	Pediatric follicular lymphoma
37203899	Nodal peripheral T-cell lymphoma with T follicular helper phenotype

	D2.2.3 – Study Protocol for C1-001	
	Author(s): [name], [name], [name], [name]	Version: 2.0 - Final
	Dissemination level: Public	

37205181	Follicular T-cell lymphoma
44806990	Follicular lymphoma grade 3a
44806991	Follicular lymphoma grade 3b

Diffuse Large B-Cell Lymphoma

Clinical description

Overview

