CLL can transform into pro-lymphocytic leukaemia (>55% peripheral blood prolymphocyte, poor prognosis) or in Richter syndrome (transformation to a high-grade large cell lymphoma). Exceptionally can lead to acute lymphoblastic leukaemia or myeloma multiple. Most patients die from the neoplasm itself and from the situation of humoral immunodeficiency (infections).

Preliminary code list

Condition domain

concept_id	concept_name
44811227	Clinical stage A chronic lymphocytic leukaemia
44811228	Clinical stage B chronic lymphocytic leukaemia
44814026	Clinical stage C chronic lymphocytic leukaemia
4082311	B-cell chronic lymphocytic leukemia
4173824	B-cell chronic lymphocytic leukemia variant
4173955	T-cell chronic lymphocytic leukemia

	D2.2.3 – Study Protocol for C1-001	
	Author(s): [name], [name], [name], [name]	Version: 2.0 - Final
	Dissemination level: Public	

4082338	Chronic lymphocytic prolymphocytic leukemia syndrome
4297353	Leukemic infiltration of skin (chronic T-cell lymphocytic leukemia)
4326339	Smoldering chronic lymphocytic leukemia
37110902	Chronic lymphocytic leukemia genetic mutation variant
37206728	Monoclonal B-cell lymphocytosis chronic lymphocytic leukemia-type
760935	Chronic lymphoid leukemia in relapse
4188973	Chronic myeloid leukemia in lymphoid blast crisis
133438	Chronic lymphoid leukemia in remission
138379	Chronic lymphoid leukemia, disease
44783718	T-cell large granular lymphocytic leukemia
132570	Leukemic reticuloendotheliosis of lymph nodes of head, face and neck
4082460	Large granular lymphocytic leukemia
193429	Leukemic reticuloendotheliosis of intra-abdominal lymph nodes
4173974	B-cell prolymphocytic leukemia
132852	Leukemic reticuloendotheliosis of extranodal AND/OR solid organ site
4082459	Hairy cell leukemia variant
4299151	Leukemic infiltration of skin in hairy-cell leukemia
4001331	Prolymphocytic leukemia (clinical)
37312023	B-cell prolymphocytic leukemia in remission
4245460	Hairy cell leukemia of spleen
4139554	Atypical hairy cell leukemia
439269	Leukemic reticuloendotheliosis of lymph nodes of axilla and upper limb
4038845	Hairy cell leukemia (clinical)
318989	Leukemic reticuloendotheliosis of lymph nodes of multiple sites
4079683	T-cell prolymphocytic leukemia
4173956	Richter's syndrome
439268	Leukemic reticuloendotheliosis of lymph nodes of inguinal region and lower limb
196650	Leukemic reticuloendotheliosis of intrapelvic lymph nodes
4173957	Splenic lymphoma with villous lymphocytes

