40483761	Acute myeloid leukemia with myelodysplasia-related changes
764781	Acute myeloid leukemia, minimal differentiation, FAB M0 in remission
764782	Acute myeloid leukemia without maturation, FAB M1 in remission
45765495	Core binding factor acute myeloid leukemia
45766268	Cytogenetically normal acute myeloid leukemia
36715587	Acute myeloid leukemia due to recurrent genetic abnormality
36717461	Therapy related acute myeloid leukemia and myelodysplastic syndrome
37110870	Acute myeloid leukemia with t(8;16)(p11;p13) translocation
37116722	Acute myeloid leukemia with t(6;9)(p23;q34) translocation
42539431	Acute myeloid leukemia with FMS-like tyrosine kinase-3 mutation
42538579	Therapy related acute myeloid leukemia due to and following administration of antineoplastic agent
35622003	Acute myeloid leukemia with NPM1 somatic mutation
35607963	Megakaryoblastic acute myeloid leukemia with t(1;22)(p13;q13)
35622696	Acute myeloid leukemia with CEBPA somatic mutations
35622760	Inherited acute myeloid leukemia
35623630	Acute myeloid leukemia and myelodysplastic syndrome related to alkylating agent
35623631	Acute myeloid leukemia and myelodysplastic syndrome related to topoisomerase type 2 inhibitor
35623633	Acute myeloid leukemia and myelodysplastic syndrome related to radiation
36683269	Acute myeloid leukemia with inv(3)(q21q26.2) or t(3;3)(q21;q26.2); RPN1-EVI1
3654662	Acute myeloid leukemia with inv(16)(p13.1q22) or t(16;16)(p13.1;q22) CFBF-MYH11
135762	Acute myeloid leukemia in remission
140352	Acute myeloid leukemia, disease
4326339	Smoldering chronic lymphocytic leukemia
4002497	Acute promyelocytic leukemia, FAB M3
4112803	Acute promyelocytic leukemia - hypogranular variant
4137687	Acute promyelocytic leukemia, FAB M3, in remission
36676614	Differentiation syndrome due to and following chemotherapy co-occurrent with acute promyelocytic leukemia
4175688	Hypergranular promyelocytic leukemia
4116880	Acute myelomonocytic leukemia - eosinophilic variant
44784490	Acute monoblastic leukemia in remission
140672	Acute monocytic leukemia in remission
4142105	Acute myelomonocytic leukemia, FAB M4, in remission
136930	Megakaryocytic leukemia in remission

	D2.2.3 – Study Protocol for C1-001	
	Author(s): [name], [name], [name], [name]	Version: 2.0 - Final
	Dissemination level: Public	

4139358	Erythroleukemia, FAB M6 in remission
4079686	Acute megakaryoblastic leukemia
138099	Erythroleukemia, FAB M6
4144191	Basophilic leukemia

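### The preliminary outcome code lists hold wrong-disease, non-specific and history codes that conflict with the protocol's own case definitions and would overcount cases if they survive the planned code review

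*Protocol*

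**What the plan says.** Section 8.6.2 defines each case by a record of the named disease and refers to a preliminary code list in Appendix I. Those lists contain the following.

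- **FL.** The condition list has "Non-Hodgkin's lymphoma (clinical" (4038838) and nine codes naming a malignant lymphoma only by site, such as "Malignant lymphoma of lymph nodes of multiple sites". The observation list has "Follicular T-cell lymphoma" (37205181) and a nodal peripheral T-cell lymphoma (37203899). Section 8.6.2 describes FL as a B-cell disease, and Appendix I says it "makes up 22% of NHL worldwide".
- **AML.** The list has "Smoldering chronic lymphocytic leukemia" (4326339, the same concept as in the CLL list) and "Myeloid leukemia in remission" (132850).
- **ALL.** The list has "Lymphoid leukemia in remission" (134596).
- **CLL.** The list has five hairy-cell codes, "Chronic myeloid leukemia in lymphoid blast crisis" (4188973) and a monoclonal lymphocytosis whose own name says it is not the CLL type (37312109).
- **Multiple myeloma.** The list has asymptomatic (4258135) and indolent (4259972) myeloma. Section 8.6.2 names smouldering myeloma as a differential diagnosis, and the criteria in Appendix I equate smouldering with asymptomatic.
- **FL and DLBCL.** Both lists hold 4146630 and 4141258, and both names contain the word follicular.
- **History codes.** These are in the myeloma (46270015), CLL (46270567) and AML (46273391) lists only.

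The abstract and section 8.1 define a 5-year prevalent case by a first diagnosis within five years. The opening of section 8.6.2 and section 8.8 run the window from the first record. The disease paragraphs of section 8.6.2 accept any relevant record in the preceding 1,825 days.

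**The concern.** Section 6 sets the purpose: to judge conditions against an orphan threshold of 5 in 10,000. When the target is rare and a listed code also covers commoner conditions, even modest contamination moves the estimate materially. FL is the clearest case, because by the protocol's own figure 78% of NHL is something else.

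The history codes raise a second problem. The 5-year estimand depends on a diagnosis date. A history entry shows that the disease occurred but does not date it, so using it as day 0 can place an old diagnosis inside the window.

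Nothing planned is certain to catch either problem. Table 5 varies prevalence type, point or period estimate, prior history and observable time, but never the outcome definition. Table 4 gives outcome validation as not applicable. The ENCePP checklist marks outcome validity (6.3) and control of outcome misclassification (10.6) the same way. Section 11 expects false positives to be uncommon, which does not fit these lists.

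**Working it through.** The protocol states no expected prevalence or precision, so there is no planned figure to reproduce. The check has three parts.

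**1. Lists against definitions.** Some conflicts can be read from the names alone: a CLL concept under AML, a lymphocytosis named non-CLL and a chronic myeloid leukaemia under CLL, and T-cell lymphomas under a disease described as B-cell. Hairy-cell leukaemia is likewise a separately named leukaemia that the CLL description does not mention. Other codes are broader than the disease: unspecified NHL, the nine site-only codes, and the two remission codes that give lineage only. Asymptomatic myeloma conflicts with the protocol's own differential diagnosis.

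**2. Possible size for FL.** Inputs:
- s = 0.22, the FL share of NHL (Appendix I), used as a proxy for its share among recorded prevalent cases;
- f = share of non-FL NHL patients caught by the generic codes. The documents do not give it, so it is assumed over a range;
- every true FL case is taken to be captured.

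Overstatement k = (s + f(1 − s))/s = 1 + f × 0.78/0.22. The true prevalence that would read as 5 per 10,000 is 5/k. The overall capture of cases at which under-recording exactly cancels the inflation is 1/k.

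| f | k | True FL per 10,000 that reads as 5 | Capture that cancels it |
|---|---|---|---|
| 5% | 1.18 | 4.25 | 0.85 |
| 10% | 1.35 | 3.69 | 0.74 |
| 25% | 1.89 | 2.65 | 0.53 |
| 50% | 2.77 | 1.80 | 0.36 |
| 100% (bound) | 4.55 | 1.10 | 0.22 |

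A narrow list has the opposite error. If a share f of true FL patients carries only a generic code, it captures 1 − f of them: 0.95, 0.90, 0.75 and 0.50 at 5%, 10%, 25% and 50%. This is why both definitions are needed.

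**3. History codes.** Suppose a patient was diagnosed T years before a history entry and has no earlier record. Under the first-record rule the patient is in the outcome cohort from year T to year T + 5 after diagnosis. For T of 5 or more, all of that time lies outside the intended window.

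The prior-history rule trims this. If the entry is made at the start of observation, the time left after the required 365 days is 1,825 − 365 = 1,460 days. With 1,095 days required it is 1,825 − 1,095 = 730 days. For 2-year prevalence with 1,095 days, the 730-day window has already closed.

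Under the alternative wording, where any relevant record in the preceding 1,825 days suffices, a history entry would also renew the window of a patient whose earlier record is visible.

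**The case against.** The strongest reply is that the lists are preliminary. Section 10 has two clinical epidemiologists judge the relevance of codes, and it uses CohortDiagnostics to consider the validity of the cohorts in each database and to inform any broad and narrow definitions. This stands to the extent that the overcount is conditional. It does not dispose of the point. Section 10 states no exclusion rule, looks explicitly for omitted codes, and only allows for broad and narrow definitions. If those are chosen after code use has been seen, the case definition depends on the data.

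Several stronger readings are tempting, but the documents do not support them.

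- *Prevalence is already inflated, or the net error must be upward.* Section 11 expects false negatives, and some true FL may be coded only as NHL. The last column of the table shows how under-recording could cancel the inflation.
- *All NHL is counted as FL.* The list holds one unspecified NHL concept and site-only codes, and the protocol does not say that descendant concepts are included. The factor 4.55 is an upper bound.
- *Chronic myeloid leukaemia as a whole enters CLL.* Only the lymphoid blast crisis code does.
- *AML could be pushed above the threshold.* The documents give no figure from which this could be shown.
- *A history code always starts a fresh five years.* Under the first-record rule it does so only when no earlier record exists. The prior-history analyses partly expose the artefact, and the quality filters on the start of observation in IPCI may reduce it there.

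Three further replies also stand. Shared FL/DLBCL codes are not in themselves an error, since the protocol says coexistence must be considered and likens grade IIIb to DLBCL. The protocol offers no basis for judging the large granular lymphocytic and leukemic reticuloendotheliosis codes. Barring every remission code would lose patients diagnosed in hospital within five years whose first primary-care entry is a remission.

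**Conclusion.** The concern holds in conditional form and should be corrected before the analysis runs. The lists contain codes that contradict the protocol's own definitions, and no planned step commits to removing them. For FL, the possible overstatement is 1.18 to 2.77 times for assumed captured shares of 5% to 50%. At 10%, a true prevalence of 3.69 per 10,000 would read as 5, so the conclusion on rarity could change.

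These figures rest on three assumptions: the worldwide 22% applies to 5-year prevalent cases in these databases, all true FL is captured, and f lies in the range shown. No single corrected prevalence can be computed from the documents, and no size can be given for AML, ALL, CLL or myeloma. The history-code problem affects three of the six cancers and is largest where the diagnosis predates the entry by five years or more. The two wordings of the window must be reconciled.

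**What to change.** 1. Delete the clear wrong-disease codes: 4326339 from AML; 37312109, 4188973 and the hairy-cell codes from CLL; 37205181 and 37203899 from FL.
2. Commit to a narrow primary definition. Move unspecified NHL (4038838), the site-only lymphoma codes, the lineage-only remission codes (132850, 134596) and asymptomatic and indolent myeloma to a broad sensitivity definition, fixed in advance and added to Table 5.
3. State how 4146630 and 4141258 are handled across FL and DLBCL.
4. Do not let history codes set the diagnosis date for 2- or 5-year partial prevalence; they may count for complete prevalence. Test disease-specific remission codes as first records in a sensitivity run rather than barring them.
5. Use one window rule in the abstract and sections 8.1, 8.6.2 and 8.8, and in the notes to Table 5.
6. Amend the statement on false positives in section 11.

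The cost is a code-list edit, a broad-definition run of a kind section 10 already contemplates, and a remission-code run. The downside is that the narrow definition will under-count FL in databases that code lymphoma only generically. The gap between the narrow and broad results shows how much rides on those codes.
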